7.3.2.2.4 Questions regarding the satisfaction with the device

At 12 and 24 months the subjects shall estimate the experience of the SP in relation to every-day situation, self-esteem, the easiness to use, durability of the device and sound quality using a Likert scale. It is a five- or seven-point scale which allows the individual to express how much they agree or disagree with a particular statement. The subjects shall also state if they are overall satisfied with the device, by answering yes or no.

7.3.2.3 Usability

7.3.2.3.1 Daily use

At the 12- and 24-months visit, data regarding daily use of the sound processor will be collected.

The estimated average hours of daily use (hours/day) during the last week before each follow up visit shall be recorded.

7.3.2.3.2 Daily streaming

At the 12- and 24-months visit, data regarding daily streaming using the sound processor shall be collected. Streaming of for example phone calls or music, can be done directly from an iOS or Android phone, or by using the wireless accessories.

Average hours of daily streaming (hours/day) during the last week before each follow-up visit shall be recorded.

7.3.2.3.3 Battery lifetime

At the 12- and 24-months visit, data regarding battery lifetime for the sound processor will be collected. Average hours of the battery lifetime for a single battery during the last week before each follow up visit. Subjects will be encouraged to use each battery until the “low battery” is signaled by the SP.

7.3.2.3.4 Magnet choice

There are 4 different magnet strengths, ranging from 1 to 4, strength 1 being the weakest. At the 12- and 24-months visit, the choice of SP magnet shall be checked and recorded. There may be a need to decrease or increase the strength depending on the subject's preference. Every time a change occurs it is important to perform a new fitting procedure according to the OFS.

7.3.2.3.5 SoftWear Pad use

At the 12- and 24-months visit, data regarding SoftWear pad use (Yes/No) for the sound processor will be collected.

7.3.2.3.6 Sound Processor retention

At the 12- and 24-months visit, the subjects shall estimate the experienced retention of the SP.

The estimation shall be performed using the VAS scale (visual analogue scale 100mm) with insufficient retention to the left and excellent retention to the right.

With regard to your Sound processor, please rate the overall retention by placing a single vertical line on the scale.

Insufficient retention	Excellent retention
-----------------------------------	--------------------------------

7.3.2.3.7 Sound Processor wearing comfort

At the 12- and 24-months visit, the subjects shall estimate the experienced wearing comfort of the SP.

The estimation shall be performed using the VAS scale (visual analogue scale 100mm) with no comfort at all to the left and excellent comfort to the right.

With regard to your Sound processor, please rate the overall comfort by placing a single vertical line on the scale.

Not comfortable at all	Most comfortable imaginable
-----------------------------------	--

7.3.2.4 Device exposure

Device exposure is information about for how long the subject is exposed to the Osia 2 Implant and the Osia 2 Sound Processor. Data is summarized from other data fields in the same case report form.

7.4 Safety Evaluations and Procedures

Subjects will be carefully monitored during the investigation for possible adverse events and appropriate treatment of the subject will be initiated. Any adverse events observed will be fully investigated by the investigator and documented in the CRF including assessment of seriousness, severity (mild, moderate or severe) and relationship to the medical device. The risks and anticipated ADEs for Osia 2 System, as identified in Section 8.2 of the CIP, will be assessed in the clinical investigation via reporting of all AEs/ADEs from the time of first subject first visit until last subject last visit. The Sponsor will be notified by automatic eCRF alerts when events are judged as device related or serious. A safety monitor, appointed by the Sponsor, will be contacted regarding events that are uncertain, serious or unexpected.

When all 12 months visits have been performed an interim safety evaluation will be performed

regarding all AEs and DDs reported. This evaluation will be performed by the team responsible for the clinical investigation, including the Safety contact/monitor. The interim safety evaluation will be documented in a report.

7.4.1 Concomitant Medication and Therapies

Relevant Medications and treatments, as judged by the Investigator, that are given to the subjects should be entered in the eCRF.

Prohibited therapies are the following:

- ototoxic drugs

If a subject receives a prohibited therapy each situation will be evaluated case by case and judged by the responsible investigator.

7.4.2 Client Service Receipt Inventory (CSRI)

CSRI is a research instrument developed to collect socio-economic information on service utilisation, income, accommodation and other cost-related variables (13). Its primary purpose is to allow resource use patterns to be described and support costs to be estimated using an appropriate unit cost. It is free to use and allows users to exclude questions not relevant for the investigation in which it is to be used.

The adapted version of CSRI will, in this investigation, collect data referent to the 12 months before each visit regarding demographics (marital status, cohabitation, usual place of residence, education level), employment status and healthcare utilisation and hearing rehabilitation.

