3 SCHEDULE OF EVENTS

Visit Type	Screening/Visit 1	EOS
Timing of Investigation	12M post-surgery	24M post-surgery
Visit window (±)	± 22 weeks	± 4 weeks
Procedures		
Written informed consent	X	
Demographics (transfer from CBAS5751)		
Eligibility	X	
Audiogram	X	X
Sound processor fitting:		
• Coil to coil measurement	X	X
• BC direct	X	X
• Fine tuning	X ^a	X ^a
Blocking verification	X	X
Free field thresholds	X	X
Speech recognition in noise	X	X
High frequency thresholds	X	X
APHAB	X	X
SSQ	X	X
HUI	X	X
Satisfaction with the device	X	X
CSRI ^b	X	X
Usability:		
Daily use	X	X
Daily streaming time	X	X
Battery lifetime	X	X
Magnet choice	X	X
Use of Soft Wear pad	X	X
Retention	X	X
Comfort	X	X
Concomitant Medications ^c	X ^d	X
Adverse Events	X ^d	X
Device Deficiencies	X ^d	X
Device exposure	X	X
Extra visits as needed		

Abbreviations: APHAB, Abbreviated Profile of Hearing Aid Benefit; SSQ, Speech, Spatial and Qualities of Hearing Scale; HUI, Health Utilities Index;

CSRI, Client Service Receipt Inventory

^a Should be performed if needed.

^b Investigates economic consequences of hearing rehabilitation by capturing major health care costs and productivity losses.

^c Specify what types of concomitant therapies are applicable e.g. prescription medications, over-the-counter medications, vitamins, and herbal supplements, and non-pharmacologic therapies such as [insert any other relevant therapies such as acupuncture, electrical stimulation, special diets and exercise regimens].

^d From the 6-months visit in the CBAS5751 clinical investigation up to the 12-months visit.

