7 DESIGN OF THE CLINICAL INVESTIGATION

7.1 General

This is a multicentre, open, long term clinical investigation evaluating safety, performance and Patient Reported Outcomes (PRO) with the Osia 2 System in adult subjects 18 years or older with conductive hearing loss, mixed hearing loss or single-sided sensorineural deafness.

The subjects are the participants who performed the 3- and/or 6-month visit in the completed CBAS5751 investigation. The maximum number of subjects will be 27 from three clinics. The subjects will be followed at two visits, 12 and 24 months after the surgery date in the CBAS5751 investigation. The visit window at the 12-month visit will be opened as much as ± 5 months. The reason for this is to enable for as many subjects as possible to be included. At the time of investigation start the seven first implanted subjects in the CBAS5751 investigation have already passed their 12-month timepoint by several months. The performance of the device is not expected to change over this time period, but if it does, it will still be captured. This approach also provides the opportunity to collect safety data from the first seven subjects. At the final and most important time point 24 months, the visit window will be narrowed to ± 4 weeks.

The subjects will attend two scheduled investigation visits over a 12-month investigation period to be assessed as described in the Schedule of Events (Section 3). At investigation visits, subjects will be evaluated through objective audiological hearing tests, patient reported outcomes, questionnaires and safety assessments. The overall outcomes are to determine the hearing performance of the Investigational device at 12 and 24 months post-surgery and compare it with the last performed measurement (3 or 6 months) in the clinical investigation CBAS5751, assessed by sound-field thresholds audiometry, [PTA4, Mean of 0.5, 1, 2 and 4 kHz] and individual frequencies [0.25, 0.5, 0.75, 1.0, 1.5, 2.0, 3.0, 4.0, 6.0 and 8.0 kHz] and Adaptive speech recognition in noise. The self-reported outcomes will also be followed-up and compared with previous reported values. Safety will be assessed by recording and summarising all AEs/ADEs and DDs. A compilation of all AEs and DDs will be performed after all subjects have completed their 12-months visit. A full clinical investigation report will be prepared after the 24-month statistical analysis has been performed.

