9.6 Safety Endpoint Analyses

Separate tabulations of AEs, ADEs, SAEs, SADEs and AESIs will be produced. AEs, ADEs and AESIs will also be produced by severity (mild, moderate or severe) and relationship (related defined as Possibly, Probably and Definitely related). Number of events, number of subjects and percent of subjects with events will be presented by System Organ Class (SOC) and term in the CTCAE or IMDRF. Which system to be used will be decided and documented before the database is locked

Device deficiency will be summarized and presented as number and percentage. Device deficiencies will be presented totally and by relationship (Sound Processor, Implant, OFS or Accessories).

Concomitant medications will be presented in patient individual listings.

Descriptives for the socio-economic data, demographics and information on service utilisation related to hearing rehabilitation will be summarized for all patients.

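### The fixed 12-month CSRI look-back, with visit 1 allowed about 7 to 17 months after surgery, makes the visit 1 summary mix subjects whose period includes the implant surgery with subjects whose period does not

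*Combined protocol and SAP*

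**What the plan says.** The CSRI is completed at both visits (section 3). Section 7.4.2 says that the adapted version will "collect data referent to the 12 months before each visit". The items cover demographics and "employment status and healthcare utilisation and hearing rehabilitation".

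Both visits are anchored to the surgery date in CBAS5751. In section 3, visit 1 is at "12M post-surgery" ± 22 weeks and EOS is at "24M post-surgery" ± 4 weeks. Section 7.1 agrees: "The visit window at the 12-month visit will be opened as much as ± 5 months", and at 24 months "the visit window will be narrowed to ± 4 weeks". It explains the wide window by late subjects: at study start, "the seven first implanted subjects in the CBAS5751 investigation have already passed their 12-month timepoint by several months".

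Health care utilisation related to hearing rehabilitation is listed as an endpoint under the safety objectives (sections 6.1 and 9.2.1). Section 9.6 plans that "information on service utilisation related to hearing rehabilitation will be summarized for all patients". Section 9.2.1 leaves estimation to a later stage, in combination with outside data. Neither section has a rule for the implant surgery, for overlapping months or for months not covered.

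Section 7.2.5 times the last visit differently, at 12 months after visit 1.

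**The concern.** A fixed look-back covers the same part of a subject's course only if the visit falls at the same time after surgery. Here visit 1 can move by about five months either way, so the operation and its aftermath are in the visit 1 count for some subjects and out of it for others. That episode uses real resources: section 4.2.2.1.2 reports two related post-operative wound infections in CBAS5751 that resolved after hospitalisation. In a sample of at most 27, a few such episodes can dominate a summary of health care use.

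Section 7.1 defends the wide window on the ground that device performance should not change over that time, and that safety data can be gained from the late subjects. Neither reason helps with a resource count whose content depends on the visit date.

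At stake is the meaning of the visit 1 summary and of anything later built on both visits: a first-year total, a two-year total, or a comparison of visit 1 with EOS. Undated recall data are hard to repair afterwards, so leaving the costing to a later stage makes collection matter more.

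**Working it through.** **Inputs.** Look-back 12 months (section 7.4.2). Visit 1 (V1) at 12 months ± 22 weeks (section 3) or ± 5 months (section 7.1). EOS at 24 months ± 4 weeks (sections 3 and 7.1). Seven late subjects and a maximum of 27 (section 7.1). One month = 365.25/12 days = 4.348 weeks.

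**Check of the plan's own figure.** 22/4.348 = 5.06 months, and 5 × 4.348 = 21.7 weeks. The two statements of the visit 1 window agree. Also, 4/4.348 = 0.92 months.

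**Permitted visit times.**
- V1: 12 − 5.06 = 6.94 to 12 + 5.06 = 17.06 months.
- EOS: 24 − 0.92 = 23.08 to 24 + 0.92 = 24.92 months.
- Interval between visits: 23.08 − 17.06 = 6.02 to 24.92 − 6.94 = 17.98 months.

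**Formulas.** The recall periods are [V1 − 12, V1] and [EOS − 12, EOS].
- Overlap = max(0, 12 − (EOS − V1)).
- Gap = max(0, (EOS − V1) − 12).
- Surgery (month 0) is inside the visit 1 period only if V1 ≤ 12.

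| V1 | EOS | Overlap | Gap | V1 period starts | Surgery in V1 period |
|---|---|---|---|---|---|
| 6.94 | 24.00 | 0 | 5.06 | −5.06 | yes |
| 6.94 | 24.92 | 0 | 5.98 | −5.06 | yes |
| 12.00 | 24.00 | 0 | 0 | 0 | on the edge |
| 14.00 | 24.92 | 1.08 | 0 | 2.00 | no |
| 15.00 | 23.08 | 3.92 | 0 | 3.00 | no |
| 17.06 | 24.00 | 5.06 | 0 | 5.06 | no |
| 17.06 | 23.08 | 5.98 | 0 | 5.06 | no |

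**Early visit 1.** Up to 5.06 of the 12 months precede surgery, leaving 12 − 5.06 = 6.94 months of post-surgery coverage.

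**Late visit 1.** The first V1 − 12 months after surgery, up to 5.06, are asked about at neither visit.

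**The seven late subjects.** 7/27 = 26%, if all consent and 27 are enrolled. The protocol does not say how many months "several" is. Assuming visit 1 at month 14 or 15, the overlap is 1.08 to 3.92 months. It vanishes only if visit 1 is no more than 0.92 months late and EOS falls correspondingly late in its window.

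**Year 2 from EOS alone.** The EOS period runs from 11.08–23.08 to 12.92–24.92 months. At either extreme it covers 12 − 0.92 = 11.08 of months 12 to 24, and 11.08/12 = 92%.

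**Section 7.2.5 against sections 3 and 7.1.** EOS at V1 + 12 lies inside 23.08 to 24.92 only if V1 is between 11.08 and 12.92. At V1 = 17.06 it would be month 29.06, and at V1 = 6.94 month 18.94. Each is 4.14 months outside the EOS window.

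**The case against.** Several counter-arguments have force.

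- **Year 2 is sound.** A reader might infer that neither a year-1 nor a year-2 total can be derived. The documents do not support that for year 2: the EOS window is narrow, so its look-back approximates months 12 to 24 to within about four weeks, whenever visit 1 took place. This stands. It is also a reason not to replace the EOS look-back by a question about use since visit 1, which would turn a near-uniform year into a recall of 6 to 18 months.
- **Nothing is double counted as planned.** A reader might infer that the planned analysis counts use twice. It does not: section 9.6 is descriptive and no sum over visits is specified. Double counting arises only if the two visits are combined.
- **The gap is permitted, not shown.** The protocol documents late subjects, not early ones. An interval of 17.98 months also does not fit the anticipated total duration of 17 months (section 7.2.5). Within 17 months the gap could be at most 17 − 12 = 5 months.
- **Section 7.2.5 would remove overlap and gap.** Taken alone, EOS 12 months after visit 1 does so. It conflicts with sections 3 and 7.1 for any subject well off month 12, and it leaves the inclusion or exclusion of surgery unchanged.
- **The form is not in the documents.** It may date contacts or identify the surgery. If so, sections 7.4.2 and 9.6 should say so.
- **Pre-operative use is not excluded by the endpoint.** Correct: the endpoint is not limited to the time after implantation. The difficulty is the mixture across subjects, not the pre-operative months in themselves.

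**Conclusion.** The concern holds for the visit 1 data. Depending on the visit date, the look-back reaches up to 5.1 months before surgery or starts up to 5.1 months after it. One summary therefore pools periods with and without the surgical episode. Exclusion of surgery is documented for up to seven of 27 subjects (26%), and overlap with the EOS period is close to certain for them. Overlap, or a gap for any subject seen early, can reach 5.1 months with EOS at month 24 and 6.0 at the window edges. A year-1 total, a 24-month total and a visit 1 to EOS contrast are unreliable as the data are specified.

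This rests on the windows in sections 3 and 7.1 being the operative ones, on the late subjects consenting, and on the unseen form having no dating or surgery flag. The number of early visits is unknown. The effect is confined to the health-economic summaries: the pass/fail criteria in section 9.1 do not use the CSRI.

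**What to change.** **Section 7.4.2.** Keep the 12-month look-back at EOS. At each visit, record the start and end of the recall period relative to surgery. For each contact, record the month and whether it was the implant surgery or its episode, a CBAS5751 or LoTeOS study visit, or other care.

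**Section 9.6.** Summarise visit 1 use without the implant surgery and study visits, and show those separately. Express it per month of post-surgery coverage, which is the smaller of V1 and 12 months (6.94 to 12). If the two visits are ever combined, count contacts in overlapping months once and report the months not covered.

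**Sections 3, 7.1 and 7.2.5.** Reconcile the two statements of when the last visit takes place.

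**Cost.** A few extra fields on the adapted form and slightly more analysis. Section 7.4.2 says that questions may be left out. That fields may be added is an inference from its being an adapted version. The change does not recover the early post-surgery months missed in late subjects, and a monthly rate still averages over different phases of recovery, so a full year-1 total remains out of reach for those subjects.

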7.5 Equipment Used for Evaluation of Performance and Safety

All tests shall be performed in a sound insulated room. Equipment used for audiological testing shall be calibrated in accordance the local procedures at each clinic. A work instruction will be provided by the time of the Site Initiation Visit.

The OFS and CDI tool together with a user manual or work instruction for the software according to current released version will be provided by the sponsor.

7.6 Sponsor Role in Conduct of the Clinical Investigation

The test set-up regarding speaker placement, sound room facility and software used at each clinic were checked and approved by the Sponsor at the previous CBAS5751 investigation. Equipment used for audiological testing shall be calibrated according to the clinic's normal standard before initiation of the investigation. Calibration certificates will be asked for by the Sponsor as part of the investigation documentation.

If needed, technical expertise will be provided in the study, for example for installation of programming software, provision of training on the software or troubleshooting with the performance of integrity tests.

8 RISKS AND BENEFITS OF THE INVESTIGATIONAL MEDICAL DEVICE AND CLINICAL INVESTIGATION

8.1 Anticipated Clinical Benefits

Most recipients of a bone conduction hearing solution will experience an improved hearing performance and quality of life compared to unaided listening.

Compared to treatment according to standard practice at the clinic, the participants in this investigation will be more closely monitored regarding the IMD and also get the opportunity to meet and interact more with the audiology team and other medical staff at the clinic. The participation will lead to better knowledge on long term performance and safety which might be beneficial for future Osia System Recipients.

8.2 Anticipated Adverse Device Effects

The Investigational device has been designed and manufactured to ensure that all risks have been reduced as far as possible. However, certain adverse device effects (ADEs) may occur even after all state-of-the-art risk control measures have been implemented and verified.

As per section 4.2.2, the subjects were implanted and provided with the Osia 2 System in the previous prospective, multicentre clinical investigation CBAS5751 where safety and performance of the Osia 2 System were tested in short term, at 3 and 6 months.

The CBAS5751 clinical investigation on the Osia 2 System showed no serious adverse events or device deficiencies related to the Implant (OSI200).

The following adverse device effects were reported in relation to the procedure; infected wound (6), muscular neck pain in region inferior to operation site (2), pain (1), ear pain (1), crust on wound (1) and hair follicle caught in wound (1).

In addition, the following adverse device effects related to the device or both the device and the procedure have been reported (to date). Pain at implant site (4), itchiness and discomfort around incision (4), infection (1), tender skin at sound processor site (1), increased tinnitus (1), discomfort due to sound processor heating up (1), prominence of the edge of the Osia implant (1), distress (1) and frustration (1). In the CBAS5751 clinical investigation numbness was evaluated separately, not reported as an AE. Around 50% of the subjects reported numbness in the implant area during the investigation.

In a clinical investigation with the first generation Osia implant and Osia Sound Processor (16) the same kind of adverse device effects were reported. In addition, headache, vertigo, neuropathic pain and three cases of warm skin when using the device were reported. The issues were transient and did not cause any suffering to the subjects. In a clinical investigation with the first generation Osia implant, but the current Osia Sound Processor (17) one adverse device event was reported; skin irritation under the SP which was resolved after a few days of not using the device and adding a SoftWear pad.

More information and details with regards to any risks with the use of the Investigational device is provided in the Investigator's Brochures (3) (4).

8.3 Risks Associated with Participation in the Clinical Investigation

The subjects are already implanted with the investigational device and using the Sound Processor, no additional risk is therefor expected for participation. The long-term risk of using the Osia System is unknown, which will be followed in this investigation in a controlled way until 24 months post implantation.

Due to the current COVID-19 pandemic it could be a potential risk for the subjects to visit the clinics in case of increased outbreaks in the respective regions.

